#### 4.4 Endpoints

##### 4.4.1 Efficacy endpoints

- Percentage of patients with controlled blood pressure (SBP  $\leq$  140 mmHg / DBP  $\leq$  90 mmHg) from baseline to 4 and 8 weeks
- Distribution of changes in HTN classification, from baseline to 4 and 8 months
- Changes in PAS, PAD, and PAM from baseline to weeks 4 and 8 between Richmond 30 mg extended-release nifedipine administered orally vs. comparator administered orally

##### 4.4.2 Safety endpoints

- Proportion of patients experiencing serious adverse events overall and by type of serious adverse event [time frame: 4 and 8 weeks]
- Proportion of patients experiencing non-serious events overall and by type of non-serious adverse event [time frame: 4 and 8 weeks]

Safety will be assessed by monitoring adverse events and laboratory tests. Subjects will be asked about any unexpected symptoms or occurrences during the study. All adverse events, regardless of severity or relationship to the study drug, will be recorded on case report forms.

The safety and tolerability of the drug will be evaluated through clinical assessment of AEs and verification of other parameters, including vital signs, physical examination, electrocardiogram, and clinical laboratory results at defined follow-up times, according to the study's SoA activity schedule.

Adverse events are evaluated and recorded according to a defined institutional procedure (P-INV-02: Adverse Events in Clinical Research). Participants may be asked to attend unscheduled visits for additional safety monitoring.

##### 4.4.3 Rationale for use of comparator

Given the notification of shortage reported by the manufacturer of the *gold* standard reference product (ADALAT OROS®), the nifedipine product with a similar galenic form that has a valid INVIMA health registration in this case, Nifedipine 30mg Extended Release, will be used as a comparator.

#### 4.5 Justification of the dose

The clinical study will evaluate the use of extended-release nifedipine at a daily dose of 30mg, established by the treating physician's clinical criteria, as monotherapy or in combination with another antihypertensive agent.

Product: 910002

### 5.2 Exclusion criteria

- Contraindication for the use of nifedipine according to the safety profile established in the literature (Investigator's Manual).
- 
- History of hypertensive encephalopathy documented in medical records.
- Evidence of secondary hypertension such as aortic coarctation, pheochromocytoma, hyperaldosteronism, except for controlled hypothyroidism-hyperthyroidism and obstructive sleep apnea
- History of a diagnosis or condition that, in the investigator's opinion, may affect patient safety.
- History of severe allergies to any drug
- Subject with heart failure, New York Heart Association (NYHA) class III or IV
- Severe coronary artery disease manifested by a history of myocardial infarction or unstable angina in the last 6 months prior to visit 1.
- Heart valve disease "Valvular heart disease with symptoms (dyspnea, syncope, or precordial pain) documented by current medical history."
- History of malignancy in the last 5 years, excluding skin or basal cell cancer
- Surgical or medical conditions that may alter the metabolism, excretion, distribution, or absorption of any drug.
  - Gastrointestinal disease or surgery that may result in malabsorption.
  - Severe narrowing of the gastrointestinal tract; Kock's pouch (ileostomy after proctocolectomy)
  - Cholestasis or biliary obstruction or history of pancreatic injury or clinically significant increase in lipase, amylase, or bilirubin.
  - Transaminase levels (AST and ALT) > 3 x ULN
  - Renal failure, defined as eGFR <30 mL/min (calculated using the Cockcroft-Gault formula) or on hemodialysis

Product: 910002

- Participation in another research trial
- Pregnant women
- Subjects with an aortic aneurysm who, in the opinion of the investigator, are not suitable for inclusion in the study.
- Considered by the investigator for any reason to be unsuitable for participation in a clinical study
- : such as everolimus and pimozone. History of noncompliance, alcoholism, or drug abuse that, in the investigator's opinion, will compromise the successful completion of the study.
- Use and indication of the following medications: alosetron, cisapride, anti-obesity preparations (fenfluramine, dexfenfluramine, phentermine), troglitazone, systemic anabolics, coagulation factors, doxazosin, terbinafine, isotretinoin, itraconazole, celecoxib, phenytoin, centrally acting sympathomimetic drugs, mefloquine, phenylpropanolamine.

### 5.3 Lifestyle restrictions

No lifestyle restrictions are required for the study procedures.

#### 5.3.1 Meals and dietary restrictions

Participants should avoid consuming grapefruit, including juices and foods containing grapefruit, due to the interaction between its components and nifedipine (see Investigator's Manual).

### 5.4 Participants who were not selected

Participants who do not pass the selection phase are defined as participants who give their informed consent to undergo screening but are not included in the study. Minimal information is required on these cases to ensure transparent reporting of the study stages in compliance with the CONSORT (Consolidated Standards of Reporting Trials) guidelines (24) and regulatory authority inquiries. Information on this group includes demographic data and criteria for non-inclusion in the study.

### 5.5 Participant replacement strategy

Participants who discontinue their participation in the study will not be replaced.

## 6 Treatment

Treatment in the study is defined as any investigational treatment, marketed product, or placebo intended to be administered to a study participant according to the study protocol.

### 6.1 Treatments administered

Product: 910002

The study treatments to be used in this trial will be provided by the sponsor and are described below:

- Richmond 30 mg extended-release nifedipine, administered orally
- Either as monotherapy or in combination with another antihypertensive agent according to the pharmacotherapeutic management established by the treating physician in accordance with the clinical history and blood pressure readings. No changes will be made to treatments within the framework of the research, and the antihypertensive combination will be maintained throughout the study period.
- Nifedipine 30 mg extended release Comparator orally
  - o As monotherapy or in combination with another antihypertensive agent according to the pharmacotherapeutic management established by the treating physician based on clinical history and blood pressure readings. No changes will be made to treatments within the framework of the investigation, and the antihypertensive combination will be maintained throughout the study period.

## 6.2 Treatment allocation method

Randomization/treatment assignment will be performed in permuted blocks at the research center by a person assigned and qualified for this activity who is not involved in the clinical evaluation of the participant, according to the following procedure (Figure 1):

- **Group A:** 8 weeks of treatment with Nifedipine Richmond New Formulation —  
-- 8 weeks of treatment with reference product (the first 2 weeks will be included for statistical silence).
- **Group B:** 8 weeks of treatment with reference product-----8 weeks of treatment with Nifedipine Richmond (the first 2 weeks will be included for statistical silence).

The random assignment method is by permuted blocks, where the random sequence will be taken between study groups A and B. The sequence will be carried out taking into account permutations 1. AB and 2. BA.

The random selection will use the random function (RANDOM: uniform distribution between 0 and 1) and the randomly selected sequence will be obtained using the equation  $\text{RANDOM} \times 2 + 1$ , taking the integer part; in the EXCEL Office 365 program.

**Table 2.** Random sequence list

Patient	Random	Randomx2+1	Sequence selected	Assigned sequence
1	0.67511186	2.350223724	2	BA
2	0.63655793	2.273115864	2	BA
3	0.82005771	2.640115417	2	BA

Product: 910002

4	0.75238537	2.504770731	2	BA
5	0.27060773	1.541215464	1	AB
6	0.13509461	1.27018922	1	AB
7	0.0059008	1.011801603	1	AB
8	0.00522046	1.01044092	1	AB
9	0.57459303	2.149186066	2	BA
10	0.13413163	1.268263257	1	AB
11	0.46855475	1.937109506	1	AB
12	0.43792582	1.875851646	1	AB
13	0.92905912	2.858118233	2	BA
14	0.76263057	2.525261134	2	BA
15	0.59039799	2.180795977	2	BA
16	0.67106409	2.342128183	2	BA
17	0.57513717	2.150274349	2	BA
18	0.95687127	2.91374253	2	BA
19	0.87915414	2.758308274	2	BA
20	0.51677593	2.033551866	2	BA
21	0.37768148	1.755362968	1	AB
22	0.13192216	1.263844313	1	AB
23	0.42201985	1.84403969	1	AB
24	0.20962522	1.419250439	1	AB
25	0.20456967	1.409139347	1	AB
26	0.65660156	2.313203122	2	BA
27	0.54821573	2.096431466	2	BA
28	0.91311981	2.826239619	2	BA
29	0.09187709	1.183754176	1	AB
30	0.66954146	2.339082914	2	BA
31	0.56996805	2.139936106	2	BA
32	0.35135826	1.702716511	1	AB
33	0.31718197	1.634363941	1	AB
34	0.42369607	1.84739214	1	AB
35	0.82200106	2.644002116	2	BA
36	0.50705857	2.014117148	2	BA
37	0.05075322	1.101506442	1	AB
38	0.03452872	1.069057445	1	AB
39	0.5778017	2.155603408	2	BA
40	0.74539157	2.490783148	2	BA
41	0.4633266	1.926653207	1	AB
42	0.6429415	2.285882992	2	BA
43	0.58347941	2.166958827	2	BA
44	0.80208274	2.604165476	2	BA
45	0.73496442	2.469928848	2	BA
46	0.37694131	1.753882624	1	AB

Product: 910002

47	0.98503347	2.970066934	2	BA
48	0.64999045	2.299980891	2	BA
49	0.38904254	1.778085075	1	AB
50	0.37535928	1.750718554	1	AB

The Principal Investigator or a member of the research team who is trained, authorized, and supervised by the PI is responsible for ensuring that randomization instructions at the research center are carried out correctly in accordance with the protocol. The investigator must follow the randomization procedures in accordance with the protocol and the randomization allocation system and must ensure that the code is only opened in accordance with the protocol. Likewise, they must keep a record of the randomization procedure, which must be recorded in the medical record, in the Investigator's File, and in the Research File (I-INV-07: Randomization of Patients for Clinical Research at Méderi).

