### 6.3 Blinding

Double-blind masking will be performed. Oral formulations will be packaged identically so that treatment masking is maintained; thus, the patient volunteer, the investigator, and the personnel involved in the clinical evaluation of the participants will not know the group assignments. The research pharmacist will have information about the coding and identification of the test and reference drugs according to the protocol for delivery of 30 mg extended-release nifedipine samples for safety and efficacy study (Appendix 6).

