#### 9.1 Summary of statistical analysis plan

Product: 910002

Design	Phase III, randomized, active-controlled clinical trial to evaluate the efficacy and safety of Nifedipine 30 mg extended-release in adult patients diagnosed with mild or moderate hypertension in Colombia.
Randomization	Permuted blocks, 1:1 ratio
Blinding	Double-blind
Analysis population	Efficacy assessment: Intention-to-treat (ITT) analysis Safety assessment: Analysis of patients treated (ASaT)
Criteria for Primary	Criteria
Secondary of assessment	Proportion of patients achieving the blood pressure control target (<140/90 mmHg) at week 4 of follow-up.  Proportion of patients experiencing serious and non-serious adverse events at week 8 of follow-up.
Statistical methods for efficacy analysis	Difference in mean SBP and DBP from baseline to weeks 4 and 8  Significance value and 95% CI for difference in mean SBP and DBP from baseline to 4 and 8 weeks between the two treatments (repeated measures ANOVA).  p-value or significance value and 95% CI for differences between the proportions of normal blood pressure readings (<140/90 mmHg) at 4 and 8 weeks between treatments using McNemar's chi-square test for differences in proportions with and without continuity correction or Fisher's exact test for paired designs (expected values < 5).
Statistical methods for safety analysis	Percentage of serious and non-serious adverse events between treatments and percentage by type of adverse event for each treatment (descriptive).
Size and power of the sample	A sample size of 50 patients is defined, each patient = 2 study subjects.

Product: 910002

For a maximum change of 3 mmHg between the two treatments, with 90% power, 95% reliability, and 10% losses, a 1:1 ratio, and a sample size of 50:50 (1 patient = 2 study subjects).

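### Table 2 prints all 50 patient-level assignments in the protocol, against its own blinding rules, and the list is simple randomisation rather than the stated permuted blocks

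*Protocol*

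**What the plan says.** Section 6.2 of the protocol states the method as follows: "The random assignment method is by permuted blocks, where the random sequence will be taken between study groups A and B". It continues: "The sequence will be carried out taking into account permutations 1. AB and 2. BA". The summary table in section 9.1 gives "Permuted blocks, 1:1 ratio". No block size across patients is stated.

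The generating rule is also in 6.2: "the randomly selected sequence will be obtained using the equation" RANDOM × 2 + 1, keeping the integer part, with RANDOM uniform between 0 and 1 and drawn in a spreadsheet. The output is printed as Table 2, "Random sequence list". It has 50 numbered patient rows, each with its random number and its assigned sequence, AB or BA.

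The key is in the same section. Group A begins with "8 weeks of treatment with Nifedipine Richmond New Formulation" and then takes the reference product. Group B begins with "8 weeks of treatment with reference product" and then takes Richmond.

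Against this, section 6.3 says that the patient, the investigator and "the personnel involved in the clinical evaluation of the participants will not know the group assignments". Appendix 6 (identification of samples) limits knowledge of the product code to two roles, the sponsor's project leader and the dispensing pharmacist. Section 8.4.2 routes emergency unblinding through the person responsible for randomisation.

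**The concern.** There are two separate faults in one section.

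**Disclosure.** The protocol treats assignment as secret and also publishes it. Section 6.2 makes the investigator follow the protocol's randomisation procedures and keep a randomisation record in the medical record and the Investigator's File. The participant card in section 11 carries the randomisation number. Someone who knows the next assignment can choose whom to enrol. Someone who knows the current drug may read blood pressure differently. The exposure is real here because section 8.3 has visit pressures read by Korotkoff sounds, and sections 8.5 and 9.3.1 judge them against a 140/90 mmHg cut-off. In a non-inferiority trial, an observer who expects no difference can pull the two products together, which favours the conclusion sought.

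**Method.** A list described as permuted blocks should keep the two sequences close to balance throughout enrolment. A separate uniform draw for each patient does not.

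**Working it through.** **1. Reproduce the plan's own list.** The inputs are the 50 random numbers printed in Table 2. The rule is INT(2u + 1), with 1 = AB and 2 = BA.

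- Patient 1: 2 × 0.67511186 + 1 = 2.3502, integer part 2, so BA.
- Patient 5: 2 × 0.27060773 + 1 = 1.5412, integer part 1, so AB.

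All 50 printed assignments equal INT(2u + 1) of their own random number. Each row is therefore an independent draw, which is simple randomisation.

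**2. Totals.** AB = 22 and BA = 28. The longest run is eight BA, patients 13 to 20.

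**3. Test for blocks.** A complete balanced block must end at a point where AB and BA are equal in number. The running tally is equal only after patients 8, 10 and 14. Patients 15 to 50 contain 22 − 7 = 15 AB and 28 − 7 = 21 BA, and the tally never returns to equality. Treating those 36 patients as one unfinished block would need a block of at least 2 × 21 = 42. The list therefore cannot be partitioned into balanced blocks, and no mix of even block sizes up to 12 reproduces it.

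| Fixed block size | Complete blocks | Balanced |
|---|---|---|
| 2 | 25 | 6 |
| 4 | 12 | 3 |
| 6 | 8 | 2 |
| 8 | 6 | 3 |
| 10 | 5 | 2 |

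Some blocks balance by chance, but no size holds throughout.

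**4. What blocking would have given.** Block size 2 gives 25:25. Block size 4 gives 12 full blocks plus two patients, so 25:25 or 24:26. The running imbalance cannot exceed half the block size (1 or 2). In Table 2 it reaches 8, at patient 48.

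**5. Cost of the 22:28 split.**

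- Relative efficiency = 4 × 22 × 28 / 50² = 2464 / 2500 = 0.986.
- Under simple randomisation, a split at least this uneven has probability 0.48, and exactly 25:25 has probability 0.112. The result is unremarkable for the method actually used.
- Let τ be the treatment difference (Richmond minus reference) and π the period effect (period 2 minus period 1). AB patients contribute τ − π and BA patients τ + π. The unadjusted mean paired difference is τ + π(28 − 22)/50 = τ + 0.12π. The documents give no value for π. This applies to mean pressures; no corresponding figure for the McNemar comparison of controlled proportions was derived.

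**6. Disclosure.** This part needs no arithmetic. Section 6.2 gives patient number, sequence and product key together, and sections 6.3 and Appendix 6 say that this information is restricted. Both cannot hold for someone who has the protocol.

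**The case against.** The strongest defence is that look-up requires a step the protocol does not spell out. Sections 8.2.6 and 8.2.7 describe a selection number, a separate randomisation number and a centralised process. Section 6.2 gives the task to someone outside the clinical evaluation. Nothing states that row n of Table 2 is the nth patient randomised. This stands as a condition on the conclusion. It does not remove the point, because no other list is described, Table 2 is not called illustrative, and its row count equals the planned sample.

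A reader might infer that the whole double blind is lost. The documents do not support that. They show the investigator working from the protocol. They do not show patients holding it, and the identical boxes and capsules (6.3 and Appendix 6) may still mask them.

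A reader might also infer that missing blocks caused the loss of concealment. They did not: unblocked draws are harder to predict than small blocks. Only printing the list matters for concealment.

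A third inference is that 22:28 breaks a promised 25:25. The protocol never promises 25:25. Sections 4.2.1 and 9.6 tie the 1:1 ratio to each patient counting as two study subjects, and a completed crossover satisfies that at any sequence split. On the same reading, permutation could mean the order of products within one patient. That explains the wording, but it is not blocking across patients, so the method is still misdescribed.

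**Conclusion.** Both faults stand, and they differ in weight.

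The printed list contradicts section 6.3 and Appendix 6 and must be corrected. If Table 2 is operative and numbered in randomisation order, all 50 assignments can be read in advance by anyone with the protocol, at least the investigator. Concealment and observer blinding are then compromised. The documents give no basis for a bias in mmHg, so none is claimed.

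The mislabelled method is certain and does not depend on that assumption: 22 AB to 28 BA, last balanced at patient 14, and no partition into balanced blocks. Its statistical cost is small, with 98.6% efficiency and a weight of 0.12 on any period effect in an unadjusted mean difference. It calls for a correction of method and wording and does not itself threaten the result.

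**What to change.** - Remove Table 2 from the protocol.
- For patients not yet randomised, generate a new list by actual permuted blocks across patients. It should be prepared outside the clinical team and held only by the research pharmacist or randomisation holder and in a sealed file.
- Correct the method description in sections 6.2 and 9.1 so that it matches what is done.
- If patients were already allocated from Table 2, say so in the report and keep them in the ITT analysis. This is possible: the document history dates version 3 to August 2023, while the synopsis expected a 2021 start, and recruitment status is not given. Include period and sequence in the treatment comparison. Where numbers allow, compare results before and after the list was replaced. Excluding the affected patients is not advisable, because it drops randomised patients and would empty the sample if Table 2 was used throughout.

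The cost is one amendment and relabelling of undispensed boxes. The sample size does not change.

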### 6.3 Blinding

Double-blind masking will be performed. Oral formulations will be packaged identically so that treatment masking is maintained; thus, the patient volunteer, the investigator, and the personnel involved in the clinical evaluation of the participants will not know the group assignments. The research pharmacist will have information about the coding and identification of the test and reference drugs according to the protocol for delivery of 30 mg extended-release nifedipine samples for safety and efficacy study (Appendix 6).

### 6.4 Preparation/handling/storage/accounting

#### 6.4.1 Dose preparation

Participants will receive blinded boxes of Nifedipine 30 mg for the study period (F-FAR-35: Research Product Dispensing).

Additionally, participants will receive the usual complementary antihypertensive management in case combination therapy is required. The dispensing of this medication will be guaranteed without modifications so as not to introduce bias into the study due to changes in the manufacturer's laboratory or administrative issues that prevent the continuity of the prescribed treatment.

Both nifedipine 30 mg [study and comparator] and concomitant antihypertensive medications will be provided by the sponsor for the conduct of the study.

#### 6.4.2 Handling, storage, and accounting

The investigator or designated person must ensure that

Product: 910002

of appropriate temperature and humidity during the handling of all study treatments received, and any discrepancies shall be reported and resolved prior to use.

Only participants included in the research may receive the study treatment, which may only be administered by personnel authorized by the research center. All treatments shall be stored in a secure area with restricted access and with the respective humidity and temperature controls recorded in accordance with the specific conditions required by the product, according to the procedures indicated in the quality document established by the research center (P-FAR-20: Receipt, Storage, Dispensing, and Inventory Control of Investigational Products). Additionally, the investigator and the research center will be responsible for accounting, reconciliation, and maintenance of study treatment records (receipt, reconciliation, and final destination registration) reported in the corresponding documentation.

The research center is responsible for the technical receipt of research products, ensuring compliance with quality requirements and recording the batch number, manufacturer, and date of all products purchased in accordance with local regulatory guidelines. It should be noted that all activities related to the receipt, storage, dispensing, and inventory control of research products are carried out in the designated area of the institution's pharmaceutical service.

The investigator is responsible for taking the necessary measures to maintain adequate records and ensure that the supply, storage, handling, distribution, and use of study treatments are appropriate in accordance with the protocol and applicable regulations.

